## **2. GENERAL ANALYSIS DEFINITIONS**

The statistical analysis will be performed using SAS® version 9.3 or higher.

The analysis will include descriptive statistics, frequency tabulations, statistical analyses, graphical presentations and data listings.

Unless otherwise specified, descriptive statistics of continuous parameters will be summarized using the following statistics: number of observations, mean, standard deviation (SD), standard error (SE), minimum, median and maximum. Frequency tabulations will display the number of subjects and corresponding percentage, where the incidence is based on the number of subjects in each treatment group.

## **Treatment Group Names**

The treatment group names will appear in the tables, figures and listings (TFLs) as:

- Placebo
- JNJ-42165279 25mg

## **Lead-In Placebo Responders**

Lead-in placebo responders are defined as subjects with  $\geq 40\%$  improvement from lead-in baseline in the HDRS17 total score at the end of the lead-in period.

Data from eCRF will be used to determine if subjects are lead-in placebo responders, since this reflects the final, clean data. For some subjects, incorrect HDRS17 total scores were fed into the IWRS system, and these scores were updated afterwards in the eCRF system (after randomization had occurred, and source data verification revealed that data had been wrongly entered into the IWRS system). A listing will be created with subjects who have HDRS17 total score discrepancies between the IWRS system and the eCRF system at lead-in baseline and at the end of the lead-in period. Data from the eCRF system will be used for the analysis.

Initially, at the time of protocol development, the lead-in placebo response definition was set at  $\geq 50\%$  improvement. However, when subject enrollment had started, it became apparent that the expected number of lead-in placebo responders was lower than what was anticipated (0 out of 14 subjects, while it was predicted to have 2-3 subjects). It was clear that out of the first set of 14 subjects, two subjects showed substantial improvement (40% and 41%) but they did not meet the  $\geq 50\%$  improvement threshold. In order to make sure that the enrichment strategy would work, it was decided to update the definition of lead-in placebo response from  $\geq 50\%$  improvement to  $\geq 40\%$  improvement. In the analysis, we will apply the 40% improvement definition to all subjects, and a listing will be created to identify the two subjects who were randomized using the 50% improvement definition. Section 3.2 describes how lead-in placebo response will be summarized.

### **2.1. Pooling Algorithm for Analysis Centers**

Centers will be pooled by country for the statistical analysis.

### **2.2. Analysis Sets**

#### **2.2.1. All Subjects Analysis Set**

The **All Subjects Analysis Set** will include all subjects who were screened.

This analysis set will be used for all listings and for calculating and listing the study execution period.

#### **2.2.2. All Enrolled Analysis Set**

The **All Enrolled Analysis Set** will include all subjects who were enrolled into the Lead-in period, regardless of whether treatment was received.

This analysis set will be used for summarizing study disposition.

### 2.2.3. Safety Analysis Set

The **Safety Analysis Set** will be defined for both enriched and full study populations.

- The Safety Analysis Set is defined as all enrolled subjects who received at least one dose of study medication in the Lead-in Period.
- The Enriched Safety Analysis Set is defined as all enrolled subjects who received at least one dose of study medication in the Lead-in Period and who were lead-in placebo non-responders.

The safety analysis set will be used for summarizing safety information. In addition, the enriched safety analysis set will be used for summarizing adverse events.

### 2.2.4. Efficacy Analysis Sets

The **ITT Analysis Set** will be defined for both enriched and full study populations. At the time of study suspension, two subjects who were randomized had to withdraw early from the study (1 placebo subject, 1 JNJ-42165279 subject, both placebo non-responders). These two subjects will not be included in the ITT analysis sets.

- The Enriched ITT (eITT) Analysis Set is defined as all enrolled subjects who were randomized into the double-blind treatment period, who were lead-in placebo non-responder, who received at least one dose of double-blind study medication and have at least one post-baseline HDRS17 assessment during the double-blind treatment period.
- The Full ITT (fITT) Analysis Set is defined as all enrolled subjects who were randomized into the double-blind treatment period, who received at least one dose of double-blind study medication and have at least one post-baseline HDRS17 assessment during the double-blind treatment period.

Efficacy analyses will be summarized for both the eITT and fITT analysis sets.

### 2.2.5. Per Protocol Analysis Set

The **Per Protocol Analysis Set** will include all eITT subjects who did not have a major protocol deviation during the study. A sensitivity analysis of the primary efficacy parameter will be performed for the per protocol analysis set.

### 2.2.6. Biomarker Analysis Set

The **Biomarker Analysis Set** will include all enrolled subjects who were randomized in the double-blind treatment period, who received at least one dose of double-blind study medication and have biomarker data available in the double-blind treatment period. The biomarker analysis set will be used for summarizing biomarker results.

### 2.3. Study Day and Relative Day

#### Screening Period

Study day in the Screening Period is calculated relative to the Lead-in Period start date. All study days in the Screening period will be negative, there is no Study Day 0:

$$\text{Study Day} = \text{measurement date} - \text{Lead-in Period start date}$$

#### Lead-in, Double-Blind Treatment and Withdrawal Periods

Study day is calculated relative to the treatment start date in the corresponding study phase. By definition, there is no Study Day 0.

$$\text{Study Day} = \text{measurement date} - \text{treatment start date} + 1$$

#### Follow-Up Period

Study day is calculated relative to the Follow-Up Period start date. By definition, there is no Study Day 0.

$$\text{Study Day} = \text{measurement date} - \text{follow-up period start date} + 1$$

### 2.4. Analysis Timepoints and Phases

Please refer to the time and events schedule in the latest version of the protocol for analysis timepoints per assessment.

**Baseline (reference time point):** for each of the Lead-in, DB Treatment and Withdrawal Period, the reference assessment, i.e. baseline, is the measurement the closest, and prior to the first study medication administration of that period. The baseline measurement may be taken from a scheduled or unscheduled visit.

**End Point for double-blind treatment period:** end point is defined as the last non-missing post-baseline observation during the double-blind treatment period. End point will be defined only for the double-blind treatment period.

Analysis phases will be constructed as follows:

Analysis Phase	Start Date/time	End Date/time
Screening	00:00 of the date of signing the informed consent	1 minute before the first study medication administration in the Lead-in Period
Lead-in Treatment Period	Date/time of the first study medication administration in the Lead-in Treatment Period	1 minute before the first study medication administration in the Double-Blind Treatment Period

		If the subject does not enter the Double-blind Treatment Period then use 23:59 of the day before the date of the first Follow-Up visit
Double-Blind Treatment Period	Date/time of the first study medication administration in the Double-Blind Treatment Period  If the subject takes the morning dose on the day of randomization prior to the randomization (i.e. a dose of the lead-in medication), the time of morning intake of the next day is not known. The start date of the double-blind treatment period will be the day after the day of randomization, and the time of intake will be imputed as 0:00.	1 minute before the first study medication administration in the Withdrawal Treatment Period.  If the subject does not enter the Withdrawal Treatment Period then use 23:59 of the day before the start of the Follow-Up period.
Withdrawal Treatment Period	Date/time of the first study medication administration in the Withdrawal Period	Day 77 visit or early withdrawal visit for subjects who dropout early.
Follow-up	00:00 of the date after the Day 77 visit or early withdrawal visit for subjects who dropout early.	23:59 of the day of study termination (date of last contact)

The last phase, whichever it is for a subject, always ends on 23:59 of the day of study termination (last contact).

In case of a dropout during a treatment phase: the dropout subject will have a follow-up phase after this phase only if a follow-up visit (as defined in the protocol) was performed.

The number of days per phase will be defined as: *day of phase end* – *day of phase start* + 1.

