Urine drug screen	X ^j	X			X			X		X	
Alcohol screen	X	X									

^a This section has been amended per Amendments INT-1, 2, 3 and 4.

Phase	Screening	Double-Blind Treatment ^a									Posttreatment ^b (Follow up)
		2	3	4	5	6	7	8	9	EW ^b	
Visit	1	2	3	4	5	6	7	8	9	10	11
Week (end of)	-4 to 0	0	1	2	3	4	5	7	9	11	12 to 14
Day	-28 to -1	1	7	14	21	28	35	49	63	77	84 to 98
Clinic Visit (C)	C	C	C	C	C	C	C	C	C	C	C
Pregnancy test	X ^k	X ^t	X ^t	X ^t	X ^t	X ^t	X ^t	X ^t	X ^t	X ^k	
Independent Central Rater assessments											
Validation of the suitability of the subject for enrolment (after review of MINI, ATRQ and HDRS ₁₇)	X										
Site Clinician-administered assessments											
HDRS ₁₇ using SIGH-D – performed by clinical site ^r	X	X	X	X	X	X	X	X	X	X	
SIGH-A - performed by clinical site		X	X	X	X	X	X	X	X	X	
CGI-I			X	X	X	X	X	X	X	X	
Patient-reported assessments											
CPFQ		X	X		X		X	X	X	X	
CUDOS-A		X	X		X		X	X	X	X	
SHAPS		X	X		X		X	X	X	X	
MOS Sleep-R		X	X		X		X	X	X	X	
PSS		X	X		X		X	X	X	X	
Self-assessment of treatment experience										X	
Pharmacokinetics											
Blood sample collection for JNJ-42165279 ¹				X			X		X	X	
Pharmacogenomics (DNA)											
CCI											
Biomarkers											
CCI											
Ongoing Subject Review											
Concomitant therapy ^p											Continuous
Adverse events											Continuous

Footnotes:

- ^a Visits should be conducted within +/-3 days of the scheduled day.
- ^b If a subject discontinues treatment before the end of the double-blind treatment phase, early withdrawal (EW) and post-treatment assessments should be obtained. Follow-up visit will take place 7 to 21 days after last dose intake or early withdrawal.
- ^c Prestudy therapy will include all medications taken within the 30 days before screening. ATRQ verified by the independent rater will be used to document the current antidepressant used by the subjects and to determine the optimal dose of the antidepressant.
- ^d Triplicate ECG at Day 1 (predose)
- ^e Supine blood pressure, pulse, and oral temperature.
- ^f Body weight will be measured with subjects lightly clothed.
- ^g Serum chemistry, hematology, coagulation and urinalysis. TSH (all subjects) and FSH (only women) at screening only.
- ^h Only in case of any clinical significant abnormalities observed at Week 11.
- ⁱ ECG should be performed prior to study drug administration, and if possible, at approximately the same time of the day as the screening ECG.

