### 5.2. Adverse Events

The verbatim terms used in the CRFs by the investigator to identify adverse events (AEs) will be coded using the current Medical Dictionary for Regulatory Activities (MedDRA) maintained by the sponsor.

Therapeutic reach is the number of days after the last dose intake that a subject is still considered to be potentially affected by study drug. For JNJ-42165279, therapeutic reach is defined as 4 days. AEs during the double-blind treatment period will be summarized using the therapeutic reach. Therapeutic reach will only be applied to the end of double-blind treatment period or to subjects who discontinue during the double-blind treatment period.

A treatment-emergent AE (TEAE) is an event that is new in onset or increased in severity following treatment initiation. Any event with a start date and time after the first dose intake will be considered treatment-emergent. An event that starts prior to and ends after the initiation of study medication will be considered treatment-emergent only if the severity increases after the start of medication. An event that starts in the withdrawal or follow up period but within the therapeutic reach of 4 days of the double-blind treatment period will be considered treatment-emergent during the double-blind treatment period. Adverse events with onset date during the withdrawal/follow-up period outside the therapeutic reach of 4 days will be summarized separately.

- The number (%) of subjects with TEAEs will be summarized by system organ class and preferred term for each treatment group and study period. A summary will be created for the most common TEAEs ( $\geq 5\%$  incidence in either treatment group). Both of these summaries will also be provided for the enriched Safety analysis set.
- In addition, TEAEs will be summarized by severity and relationship to study drug for each treatment group and study period by system organ class and preferred term. For the summaries of AEs by severity/relationship to study drug, the observation with the most severe occurrence/closest relationship to study drug will be chosen if there is more than one incident of an adverse event reported during the treatment phase by the subject.

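### SAP 2.4 can place a lead-in dropout's days in two phases, and SAP 5.2 does not state that its 4-day reach ends double-blind adverse event counting for dropouts

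*SAP*

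**What the plan says.** The phase table in SAP 2.4 sets these ends and starts for subjects who leave early:

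- Lead-in row, subject not randomised: "If the subject does not enter the Double-blind Treatment Period then use 23:59 of the day before the date of the first Follow-Up visit".
- Double-blind row, subject not entering withdrawal: "If the subject does not enter the Withdrawal Treatment Period then use 23:59 of the day before the start of the Follow-Up period".
- Follow-up row, start: "00:00 of the date after the Day 77 visit or early withdrawal visit for subjects who dropout early".
- Below the table: "The last phase, whichever it is for a subject, always ends on 23:59 of the day of study termination (last contact").
- Condition for having a Follow-up phase at all: "the dropout subject will have a follow-up phase after this phase only if a follow-up visit (as defined in the protocol) was performed".

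The Protocol's Time and Events Schedule, footnote b, asks early leavers for early withdrawal assessments and also for a later visit: "Follow-up visit will take place 7 to 21 days after last dose intake or early withdrawal". Protocol 10.2 and 10.3 likewise ask for the end-of-treatment assessments and, in addition, a follow-up visit.

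SAP 5.2 defines the reach: "Therapeutic reach is the number of days after the last dose intake that a subject is still considered to be potentially affected by study drug". It sets the reach at 4 days and limits its use to the end of the double-blind period and to subjects who discontinue during it. It counts any event starting after first dose as treatment-emergent. It brings events from the withdrawal or follow-up period into the double-blind table if they fall within 4 days, and puts later events from those periods in a separate summary.

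**The concern.** Each adverse event should fall in one study period, because SAP 5.2 tabulates events by period. Two rules in SAP 2.4 work against this for early leavers.

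First, the end of lead-in is tied to the follow-up visit and the start of Follow-up to the early withdrawal visit. A subject with both visits is in two phases between them, and the SAP gives no rule for choosing. Lead-in dropouts are in the Safety Analysis Set (SAP 2.2.3), so their events are tabulated.

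Second, a double-blind dropout with no follow-up visit stays in the double-blind phase until last contact, however long after the last dose. The SAP's own definition says the drug's effect is considered only up to 4 days after that dose. If the phase dates alone drive the tables, events well beyond the reach appear as double-blind treatment-emergent. Two programmers could reasonably produce different counts.

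**Working it through.** The plan states no figure on this point, so there is none to reproduce. The check is day arithmetic on the stated rules.

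**Inputs**

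- Lead-in end, follow-up start, last-phase rule, and the condition for having a follow-up phase: SAP 2.4.
- Follow-up visit 7 to 21 days after last dose or early withdrawal: Protocol, Time and Events Schedule, footnote b.
- Lead-in dropout of 10% and 143 subjects entering: SAP 1.4.
- Reach of 4 days from last dose: SAP 5.2.
- Gap from last dose to the early withdrawal visit or last contact: not given, so the values below are assumptions.

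**Lead-in overlap**

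Let E be the day of the early withdrawal visit and F the day of the follow-up visit. Lead-in ends on day F − 1 and Follow-up starts on day E + 1. The overlap is max(0, (F − 1) − (E + 1) + 1) = max(0, F − E − 1).

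| Interval counted from | F − E | Overlap, days |
|---|---|---|
| Early withdrawal; 7, 14, 21 days | 7, 14, 21 | 6, 13, 20 |
| Last dose, early withdrawal 3 days later | 4, 11, 18 | 3, 10, 17 |
| Last dose, early withdrawal 7 days later | 0, 7, 14 | 0, 6, 13 |

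Example: last dose Day 10, early withdrawal visit Day 11, follow-up visit Day 25. Lead-in ends on Day 24 and Follow-up starts on Day 12, so Days 12 to 24 (13 days) are in both phases.

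Subjects exposed: 0.10 × 143 = 14.3, about 14. This is a ceiling, because a lead-in dropout with no follow-up visit has no follow-up phase and hence no overlap.

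With the double-blind row's wording, lead-in ends on day E, and the overlap is E − (E + 1) + 1 = 0 in every case.

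**Double-blind days beyond the reach**

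With no follow-up visit and last contact c days after last dose, days beyond the reach are max(0, c − 4). For c = 7, 14, 21, 30 this gives 3, 10, 17, 26 days.

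With a follow-up visit, the phase ends on the early withdrawal day, g days after last dose, and days beyond the reach are max(0, g − 4). This is 0 for g up to 4, 3 for g = 7 and 10 for g = 14. This case matters only if the early withdrawal visit is late.

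Set side by side, the definition in SAP 5.2 counts from last dose, but its working rules act only on events already placed in the withdrawal or follow-up period. A subject without a follow-up phase has no such events, so no rule moves any event out of the double-blind table. With a stated cap at last dose plus 4 days, days beyond the reach are 0 by definition.

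**The case against.** The best counter-argument is that SAP 5.2 already settles the second part. It says double-blind events will be summarised using the reach, counts the reach from last dose, and names double-blind discontinuers among those it applies to. That can fairly be read as a cap at last dose plus 4 days. It follows that SAP 2.4 does not contradict the reach: SAP 2.4 assigns all data to phases, and the reach is an adverse event rule. This stands as a reading of intent. It does not supply the missing step, because the operative sentences only bring events in or separate events already outside the period.

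On the first part, one might take the follow-up visit to mean the early withdrawal visit, which would remove the overlap. SAP 2.4 refers to the follow-up visit as the protocol defines it, and there the two are separate. It is also true that SAP Table 1 places no scheduled visit between the two, so scheduled laboratory, ECG, vital sign and HDRS17 data are not assigned twice. The exposure is essentially adverse events starting in the gap.

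A reader might infer that the comparison between arms is distorted. The documents do not support that. Lead-in dropouts received only placebo and were never randomised. For double-blind dropouts, the plan gives neither the number without a follow-up visit nor any reason to expect more in one arm. Completers also contribute up to 4 days after the double-blind period under SAP 5.2, so time off drug does not come from dropouts alone. A reader might also multiply 14 subjects by 20 days and treat the product as an estimate. It is only a ceiling: it needs every dropout to attend both visits at the longest interval, and Protocol 10.3 lists loss to follow-up and withdrawn consent among the reasons for leaving.

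**Conclusion.** Wrong as written (minor). The lead-in and follow-up rows conflict for any lead-in dropout whose follow-up visit falls at least two days after the early withdrawal visit. The overlap is 0 to 20 days per subject, depending on whether the 7 to 21 days run from last dose or from early withdrawal, and it concerns at most about 14 subjects at the planned dropout. The consequence is that an adverse event can qualify for two period tables; no comparison between arms is involved.

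The double-blind part is an incomplete rule. It bites only when a discontinuing subject's phase end (last contact, or a late early withdrawal visit) lies more than 4 days after the last dose. The documents set no limit on that gap, so the 3 to 26 days shown are illustrations. Adverse event summaries are descriptive, and the primary HDRS17 analysis does not depend on these adverse event counts.

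**What to change.** In the Lead-in row of SAP 2.4, for subjects who do not enter double-blind, replace the reference to the follow-up visit with the double-blind row's wording, so that lead-in ends on the day before the Follow-up phase begins.

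In SAP 5.2, add one sentence: for subjects who discontinue in the double-blind period, adverse events starting more than 4 days after the last double-blind dose go in the separate withdrawal/follow-up summary, whether or not a follow-up visit took place.

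Leave the assignment of HDRS17 visits unchanged. The cost is two wording edits in the SAP and one programming rule for the adverse event tables. No new data are needed.

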## 2.5. Visit Windows

As subjects do not always adhere to the protocol visit schedule, the following rules are applied to assign actual visits to analysis visits. Listed in Table 1 are visit windows and the target days for each visit. The reference day is Study Day 1 for each of the lead-in, the double-blind treatment and the withdrawal period.

If a subject has 2 or more actual visits in one visit window, the visit closest to the target day will be used as the protocol visit for that visit window. The other additional visit(s) will not be used in the summaries or analyses. If 2 actual visits are equidistant from the target day within a visit

window, the later visit is used. If a visit window has no scheduled visits but does have unscheduled visits, then the unscheduled visit closest to the scheduled visit will be used.

All assignments will be made in chronological order. Once a visit date is assigned to a visit window, it will no longer be used for a later time point except for the endpoint. Listed below (Table 1) are the visit windows and the target days (if applicable) for each visit defined in the protocol.

Table 1 – Visit Windows

Parameter	Scheduled Visit Number	Time Interval (label on output)	Time Interval (Day) 	Target Time Point (Day) by Period	Analysis Phase
HDRS 17 , C-SSRS	1	Screening	< 1	-28 to -1	Screening
	2	Lead-in Baseline	<=1	1	Lead-in
	3	Lead-in Week 1	2 to 10	7	Lead-in
	4	Lead-in Week 2	11 to 17	14	Lead-in
	5	Lead-in Week 3	18 to 24	21	Lead-in
	5	DB Treatment Baseline	<=1	1	DB Treatment
	6	DB Treatment Week 1	2 to 10	7	DB Treatment
	7	DB Treatment Week 2	11 to 21	14	DB Treatment
	8	DB Treatment Week 4	22 to 35	28	DB Treatment
	9	DB Treatment Week 6	36 to 49	42	DB Treatment
		DB Treatment End Point 			DB Treatment
	9	Withdrawal Baseline	<=1	1	Withdrawal
	10	Withdrawal Week 2	2 to 20	14	Withdrawal
CPFQ, CUDOS-A, SHAPS, MOS Sleep-R, PSS	2	Lead-in Baseline	<=1	1	Lead-in
	3	Lead-in Week 1	2 to 14	7	Lead-in
	5	Lead-in Week 3	15 to 28	21	Lead-in
	5	DB Treatment Baseline	<=1	1	DB Treatment
	7	DB Treatment Week 2	2 to 21	14	DB Treatment
	8	DB Treatment Week 4	22 to 35	28	DB Treatment
	9	DB Treatment Week 6	36 to 49	42	DB Treatment
			DB Treatment End Point 		
	9	Withdrawal Baseline	<=1	1	Withdrawal
	10	Withdrawal Week 2	2 to 20	14	Withdrawal
SATE	10	Withdrawal Week 2	2 to 20	14	Withdrawal
SIGH-A	2	Lead-in Baseline	<=1	1	Lead-in
	3	Lead-in Week 1	2 to 10	7	Lead-in
	4	Lead-in Week 2	11 to 17	14	Lead-in
	5	Lead-in Week 3	18 to 24	21	Lead-in
	5	DB Treatment Baseline	<=1	1	DB Treatment
	6	DB Treatment Week 1	2 to 10	7	DB Treatment
	7	DB Treatment Week 2	11 to 21	14	DB Treatment

Parameter	Scheduled Visit Number	Time Interval (label on output)	Time Interval (Day) 	Target Time Point (Day) by Period	Analysis Phase
	8	DB Treatment Week 4	22 to 35	28	DB Treatment
	9	DB Treatment Week 6	36 to 49	42	DB Treatment
	9	DB Treatment End Point 			DB Treatment
	9	Withdrawal Baseline	<=1	1	Withdrawal
	10	Withdrawal Week 2	2 to 20	14	Withdrawal
CGI-I	3	Lead-in Week 1	2 to 10	7	Lead-in
	4	Lead-in Week 2	11 to 17	14	Lead-in
	5	Lead-in Week 3	18 to 24	21	Lead-in
	5	DB Treatment Baseline	<=1	1	DB Treatment
	6	DB Treatment Week 1	2 to 10	7	DB Treatment
	7	DB Treatment Week 2	11 to 21	14	DB Treatment
	8	DB Treatment Week 4	22 to 35	28	DB Treatment
	9	DB Treatment Week 6	36 to 49	42	DB Treatment
	9	DB Treatment End Point 			DB Treatment
	9	Withdrawal Baseline	<=1	1	Withdrawal
	10	Withdrawal Week 2	2 to 20	14	Withdrawal
Physical Examination	1	Screening	< 1	-28 to -1	Screening
	10	Withdrawal Week 2	2 to 20	14	Withdrawal
	11	Follow Up	> DB or >Withdrawal	7 to 21	Follow Up
Neurological Examination	1	Screening	< 1	-28 to -1	Screening
	7	DB Treatment Week 2	2 to 21	14	DB Treatment
	9	DB Treatment Week 6	22 to 49	42	DB Treatment
	10	Withdrawal Week 2	2 to 20	14	Withdrawal
Vital Signs, Body Temperature, Body Weight, Clinical Laboratory Assessments, 12-lead ECG	1	Screening	<1	-28 to -1	Screening
	2	Lead-in Baseline	<=1	1	Lead-in
	3	Lead-in Week 1	2 to 14	7	Lead-in
	5	Lead-in Week 3	15 to 28	21	Lead-in
	5	DB Treatment Baseline	<=1	1	DB Treatment
	7	DB Treatment Week 2	2 to 21	14	DB Treatment
	8	DB Treatment Week 4	22 to 35	28	DB Treatment
	9	DB Treatment Week 6	36 to 49	42	DB Treatment

Parameter	Scheduled Visit Number	Time Interval (label on output)	Time Interval (Day) 	Target Time Point (Day) by Period	Analysis Phase
	9	DB Treatment End Point 	<=1	1	DB Treatment
	10	Withdrawal Baseline	2 to 20	14	Withdrawal
	11	Withdrawal Week 2 Follow Up 	> DB or >Withdrawal	7 to 21	Withdrawal Follow Up

CCI

 Relative to Study Day 1 in each of the Lead-in, the double-blind treatment and the withdrawal period

 End Point is defined as the last non-missing post-baseline measurement during the double-blind treatment period.

 For clinical laboratory assessments and ECG, the follow up visit is performed only in case of any clinical significant abnormalities observed at Week 11.

